7.3.4 Clinical Laboratory Analyses

Samples will be collected at the time points specified in [Appendix 13.1](#).

Any clinically significant abnormal laboratory test results are to be recorded as AEs or SAEs per CTCAE Version 4.0.

7.3.4.1 Hematology

Complete blood count (CBC) includes WBC with a 5-part differential, platelet count, hemoglobin, hematocrit, and ANC. Coagulation panel includes prothrombin time (PT) expressed in seconds, International Normalized Ratio (INR), and partial thromboplastin time (PTT). Patients taking coumarin-derivative anticoagulants should be monitored closely and their anticoagulant dose adjusted as needed.

7.3.4.2 Biochemistry

Biochemistry includes alanine aminotransferase, aspartate aminotransferase, gamma-glutamyl transferase, alkaline phosphatase, amylase, lipase, total bilirubin, sodium, potassium, calcium, magnesium, blood urea nitrogen or urea, carbon dioxide/bicarbonate, chloride, creatinine, creatine phosphokinase, total protein, albumin, glucose, triglycerides, total cholesterol, phosphorus, and lactate dehydrogenase. At Day 1 of each cycle, biochemistry will include creatinine clearance (calculated using the Cockcroft and Gault 1976 formula).

7.3.4.3 Urinalysis

Urinalysis analytes will include pH, protein, specific gravity, glucose, ketones, bilirubin, nitrites, and occult blood. The urinalysis may be performed using a urine dipstick.

7.3.4.4 Additional Renal Function Studies

Urine will be collected for testing of biomarkers suggestive of potential renal injury (aquaporin-2, calbindin D28, and clusterin). Analysis of this additional urine sample will be performed at a central laboratory (instructions provided in the Laboratory Manual).

7.3.4.5 Additional Microbiological Serological studies

Patients will be regularly examined and asked whether they have been suffering from an infection during their participation in the trial. If there is a reasonable suspicion that such infection could have been caused by one of the pathogens listed below, appropriate microbiological workup must be conducted. Should such workup indicate that infection was indeed caused by one of these microorganisms, re-dosing must be delayed so that there is at least a four-week window between symptom resolution and the next dose of ADCT-301.

Pathogens of interest are: HSV1, HSV2, VZV, EBV, CMV, measles, Influenza A, Zika virus, Chikungunya virus, mycoplasma pneumonia, Campylobacter jejuni, and enterovirus D68.

7.3.5 Electrocardiograms

On Day 1 of Cycles 1 and 2, a 12-lead ECG will be performed before the start of the ADCT-301 infusion, at completion of infusion and at 3 hours and 24 hours (Day 2) after the end of infusion. ECGs should occur within 10% of nominal time (e.g., 3 hours \pm 18 minutes). Any abnormalities, including those that worsen from baseline, believed to be clinically significant in the medical and scientific judgment of the Investigator are to be recorded as AEs or SAEs.

Measurement of the QTc interval may be obtained according to the formula used by the institution, however, the Fridericia formula is preferred.⁵ The same formula used to confirm eligibility must be applied within a patient for the duration of the study.

7.3.6 Physical Examination

Physical examinations will include a complete review of body systems, including whole body skin assessment. Whole body skin assessment does not have to be performed by a dermatologist; however, any unexplained lesion will be referred to a dermatologist for further evaluation and biopsy if clinically warranted. Physical examination will also include a neurological examination of strength, sensation, and deep tendon reflexes; unexpected findings will be referred to a neurologist for further evaluation. Height will be measured at the Screening Visit (Day -28 to -1) and patients are advised to monitor their weight on a daily basis because new or worsening edema and / or new or worsening pleural effusion have been observed. Patients should inform their Investigator if their weight increases by more than 1 kg (2.2 pounds) after Cycle 1 Day 1.

The examination must include a determination if the patient has had any infection. At the discretion of the investigator, evaluation of any reported infection must be conducted to rule out infection with a microorganism that may be associated with autoimmune or neurological disease(s) as specified in the exclusion criteria.

Any clinically significant abnormalities, including those that worsen from baseline, are to be recorded as AEs or SAEs.

7.3.7 Vital Sign Measurements

Vital sign measurements will include arterial blood pressure, heart rate, respiratory rate, and temperature. Any clinically significant abnormalities, including those that worsen from baseline, are to be recorded as AEs or SAEs.

7.3.8 Eastern Cooperative Oncology Group Performance Status

The patient's performance status will be assessed according to the time points in the schedule of events ([Appendix 13.1](#)) using the ECOG performance status grades⁹ below:

| | |
|----|---|
| 0: | Fully active, able to carry on all pre-disease performance without restriction |
| 1: | Restricted in physically strenuous activity but ambulatory and able to carry out work of a light or sedentary nature, e.g., light house work, office work |
| 2: | Ambulatory and capable of all self-care but unable to carry out any work activities. Up and about more than 50% of waking hours |
| 3: | Capable of only limited self-care, confined to bed or chair more than 50% of waking hours |
| 4: | Completely disabled. Cannot carry on any self-care. Totally confined to bed or chair |
| 5: | Dead |

7.4 Sample Handling, Storage, and Shipment

Detailed instructions for central laboratory sample collection, labeling, processing, storage, and shipping will be provided to the site in the central Laboratory Manual.

During the study, whole blood samples will be collected for PK, ADA, pharmacodynamics (PBMC subset analysis), and safety analyses (clinical chemistry, [REDACTED], and hematology).

For PK, ADA, [REDACTED] blood samples are to be collected and processed on site according to the Laboratory Manual. The resulting serum samples should be aliquoted and stored frozen at $\leq -70^{\circ}\text{C}$ until shipment. Each sample tube must be clearly labeled with the following information: study number, study center number, patient number, tube identification, and the sample collection time point (by day and hour), when necessary.

Serum and urine samples are to be packed in sufficient dry ice and shipped from the study center to the central laboratory. Once labeled, samples should be stored at $\leq -70^{\circ}\text{C}$ until shipment. Samples should be shipped according to the sample shipment schedule provided

in Laboratory Manual. [REDACTED]

The clinical chemistry and hematology samples, which should not be frozen, are transferred at ambient temperature to local laboratories.

For the PBMC subset analysis, whole blood is to be collected and shipped as per the central Laboratory Manual directly to the testing laboratory for immediate processing.

8 Statistical and Analytical Plan

Full details of the analysis plan, including a more technical and detailed elaboration of the statistical analyses will be provided in the Statistical Analysis Plan (SAP). [REDACTED]

8.1 Safety Endpoints

Safety will be assessed based on AEs, SAEs (graded using CTCAE v4.0), treatment discontinuations due to AEs, DLTs, hematology, coagulation panel, biochemistry, pregnancy testing (for women of child-bearing potential) and urinalysis test results. Additional safety assessments include periodic 12-lead ECG recordings, physical examinations, vital sign measurements, and ECOG performance status. A schedule of the safety assessments is provided in [Appendix 13.1.1](#).

8.2 Study Endpoints

8.2.1 Primary Endpoints

The primary objectives for Part 1 (dose escalation) and Part 2 (expansion) of the study are:

- Determine the safety of ADCT-301 by assessing DLTs and determining the MTD in Part 1 (dose-escalation).
- Determine the recommended dose of ADCT-301 for Part 2 (expansion).
- Evaluate the safety and tolerability of ADCT-301 in patients with relapsed/refractory lymphoma in Part 2 (expansion).

8.2.2 Secondary Endpoints

The following secondary endpoints will be determined in Part 1 and Part 2:

- Evaluate response to ADCT-301 using the Lugano Classification Criteria (2014) ([Appendix 13.2](#)) and Global Response Score Grading Scales for CTCL ([Appendix 13.3](#)) through the evaluation of complete response (CR), partial response (PR), progressive disease (PD), and stable disease (SD).
- Characterize PK profile of HuMax-TAC (total antibody; drug-to-antibody ratio [DAR] ≥ 0), PBD-conjugated HuMax-TAC (DAR ≥ 1), and free warhead SG3199 (see [Section 8.6.3](#)).
- Determine anti-drug antibodies ADAs in blood before, during, and after treatment with ADCT-301.

[REDACTED]

[REDACTED]

[REDACTED]

[REDACTED]

[REDACTED]

[REDACTED]

8.3 Sample Size Calculations

This is a Phase 1 study with a total sample size of approximately 140 patients. It is expected that Part 1 will enroll approximately 80 patients, and Part 2 will enroll approximately 60 patients ([Section 4.1.1](#) and [Section 4.1.2](#)).

Simulations were performed assuming scenarios with different dose-toxicity relationships to evaluate the sample size for Part 1.

Patients will be enrolled in Part 2 of the study in cohorts of approximately 10. The cohorts will be enrolled at the dose level recommended in Part 1.

The DESC will make recommendations with regard to the intended differences between these cohorts, e.g. tumor subtypes, dosing regimen or dose levels, as well as the number of these cohorts, taking into account the limit on the overall number of patients as specified above and safety/efficacy data observed up to that decision point.

8.4 Analysis Sets

Five analysis sets will be used in this study:

- The Safety analysis set consists of all patients who receive study drug
- The DLT-evaluable analysis set consists of all patients in Part 1 who receive study drug and excludes patients who discontinue from the study during the first 21-day cycle without experiencing a DLT.
- The Efficacy analysis set will consist of all patients with valid baseline data who receive at least 2 doses of study drug or who have documented progression of disease at any time after the first dose of study drug. Patients who do not have a post baseline assessment due to early clinical progression, toxicity, or death will also be included.
- The PK analysis set consists of all patients who receive study drug and have sufficient concentration data for PK analysis.

- The pharmacodynamic analysis set consists of all patients who receive study drug and have sufficient concentration data for pharmacodynamic analysis.

8.5 Description of Subgroups to be Analyzed

Subgroup analyses, if planned, will be described in the SAP.

8.6 Statistical Analysis Methodology

8.6.1 Efficacy Analysis

8.6.1.1 Overall Response Rate

Overall response rate is defined as the proportion of patients with best overall response of PR or CR at the time each patient discontinues treatment with ADCT-301 ([Appendix 13.2](#), [Appendix 13.3](#)).

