4.1 Study Design

This is a Phase 1, FIH, open-label, dose-escalation (Part 1) and expansion (Part 2) study of ADCT-301 in patients with relapsed and refractory lymphoma. The study will evaluate the safety and tolerability of ADCT-301 as monotherapy, as well as the preliminary activity, PK, pharmacodynamics, and formation of ADAs of ADCT-301 in patients.

For each patient, the study will include a screening period (up to 28 days), a treatment period (until progressive disease, intolerable toxicity, or withdrawal of consent), and a follow-up period to assess disease progression and survival for up to 12 months after the last dose of study drug. The total study duration will be dependent on overall patient tolerability to the study drug and response to treatment. It is anticipated that the entire study (Parts 1 and 2) could last approximately 3 years from first patient treated to last patient completed.

In Part 1, patients will receive ADCT-301 administered as a 1-hour IV infusion on Day 1 of each 3-week (21-day) cycle. If ADCT-301 is well tolerated after the first cycle, the infusion duration may be shortened to 30 minutes for subsequent cycles at the Investigator's discretion.

The first patient at each dose level will be monitored for any AEs for 7 days before proceeding with dosing for the second patient.

The initial dose level for Part 1 will be 3 µg/kg (Dose Level 1). The highest allowed dose will be 300 µg/kg. The MTD will be the highest safe dose that has at least a 60% probability that the dose-limiting toxicity (DLT) rate is < 30%.

After discontinuation of treatment, patients without documented objective disease progression will be followed until progression of disease or initiation of new anticancer therapy for up to 12 months. All patients will be followed for survival (by telephone contact or retrospective chart review) until a new anticancer therapy is initiated or for up to 12 months after treatment discontinuation.

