5.1.6 Long-term Follow-up

Patients who discontinue treatment for any reason other than objective disease progression will continue to be followed with scans approximately every 12 weeks from the last tumor assessment until disease progression, or initiation of new anticancer treatment. If a patient discontinues treatment for a hematopoietic stem cell transplant, the frequency of imaging will be as per the transplant center standard of care.

After documentation of disease progression or start of new anticancer treatment, patients will be contacted by telephone approximately every 12 weeks for up to 12 months after the last dose of study drug to collect survival information.

Blood Sample Collection and Adverse Event Monitoring During Long-Term Follow-up

For all patients, PK and ADA blood sample collection will be performed 12 weeks (\pm 1 week) following the last dose of ADCT-301, unless a new anticancer treatment has been initiated.

Patients who test positive for ADAs may be requested to supply additional ADA samples.

For all patients, collection of AEs and SAEs will continue for 12 weeks after the last dose of study drug or initiation of new anticancer treatment (see [Section 7.3.2.2](#)).

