### **3.3 Modifications to the statistical section of the protocol**

The efficacy analysis set was defined in the protocol as all patients with valid baseline data who receive at least 2 doses of study drug or who have documented progression of disease at any time after the first dose of study drug. The efficacy analysis set is updated in the SAP to include all patients who have received at least one dose of ADCT-301 with a valid baseline and at least one valid post-baseline disease assessment or patients who have documented progression of disease or death at any time after the first dose of study drug.

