#### **4.9.1 Overall Response Rate**

Overall response rate is defined as the proportion of patients who achieve either CR or PR as best overall response as assessed by investigators according to the Lugano Classification criteria or Global Response Score Grading Scales for CTCL patients before the start of subsequent anticancer therapy or procedure.

The order of overall response category is: CR, PR, SD, NE, PD (including disease recurrence/relapse). The overall response category will be derived based on response assessment performed on or before the start of subsequent anticancer therapy/procedure. Patients without documented subsequent anticancer therapy and/or with missing start date of anticancer therapy will be considered as not having received subsequent anticancer therapy. If a patient only has one valid disease assessment which is SD, and the assessment is within 35 days after the first dose, the overall response for this patient will be considered as NE.

The overall response rate and the corresponding 95% two-sided exact confidence interval at each dose level will be presented. Subgroup analysis may be provided if relevant.

Percent change from baseline in the sum of product of diameters (SPD) for target lesions for non-CTCL patients and mSWAT total score for CICL patients will be presented for available data in the efficacy analysis set by dose level. These data will also be displayed as a waterfall plot, with vertical bars representing the sorted values of best percent reduction for each patient.

Tumor response and lesion measurement (or mSWAT) will be listed by assessment visit.

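### ORR is taken at treatment discontinuation in the protocol but runs to the next therapy in the SAP, with no cut at progression, and SAP 3.3 does not list the difference

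*Protocol*

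**What the plan says.** Protocol 8.6.1.1 defines ORR as the proportion of patients whose best response is PR or CR "at the time each patient discontinues treatment with ADCT-301". SAP 4.9.1 uses a different end point for the window: "The overall response category will be derived based on response assessment performed on or before the start of subsequent anticancer therapy/procedure". It also gives a ranking, "The order of overall response category is: CR, PR, SD, NE, PD (including disease recurrence/relapse"), and says nothing about the order in which these categories occur. A patient "with missing start date of anticancer therapy will be considered as not having received subsequent anticancer therapy", so in that case the window stays open.

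After treatment stops for any reason other than objective progression, Protocol 5.1.6 says patients "will continue to be followed with scans approximately every 12 weeks from the last tumor assessment until disease progression, or initiation of new anticancer treatment". Protocol 4.1 adds that those without documented objective progression "will be followed until progression of disease or initiation of new anticancer therapy for up to 12 months".

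SAP 3.3 is the section that records departures from the protocol's statistical section. Its only entry concerns the analysis population: "The efficacy analysis set is updated in the SAP to include all patients who have received at least one dose of ADCT-301", with further conditions on assessments. The response window is not mentioned.

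For PFS and DOR, SAP 4.9.2 and 4.9.4 treat clinical progression recorded at end of treatment or end of study as an event, alongside radiographic progression.

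**The concern.** There are two separate problems.

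First, the two documents can give two different numerators. A patient who stops for toxicity while in stable disease and first reaches PR on a later off-treatment scan is a responder under the SAP and a non-responder under the protocol. A reader who looks in SAP 3.3 for changes will not find this one.

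Second, the SAP has no rule that closes the response window at progression. Because CR and PR outrank PD regardless of timing, a later response overrides an earlier progression. The same patient can then have a PFS event and afterwards count as a responder, and the DOR definition does not work for that patient. Nothing in the SAP tells the programmer what to do, so the choice would be made with the data in view.

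At stake are the meaning of the reported response rate and its consistency with PFS and DOR. SAP section 4 plans no hypothesis test, so no error rate is affected.

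**Working it through.** The documents give no ORR target, power or ORR-based sample size, so there is no figure to reproduce. The check compares the texts and then sizes the effect.

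**1. The gap between the windows.** The protocol window closes when ADCT-301 stops. The SAP window closes at the next anticancer therapy or procedure. Between the two lie the off-treatment scans. Twelve months is about 52.2 weeks, and 52.2 / 12 = 4.35, so about four scheduled assessments fall inside the SAP window and outside the protocol's.

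**2. Routes to a response after progression under the SAP.**
- *Objective PD in ordinary conduct.* The treatment period is described as "a treatment period (until progressive disease, intolerable toxicity, or withdrawal of consent"). On-treatment assessments run until progression (Protocol 5.1.2, 7.1), and off-treatment scans are only for patients who stopped without objective progression (5.1.6). No later scan is scheduled, so this is not a normal route.
- *Clinical progression at end of treatment.* This is a PFS and DOR event in the SAP, but it is not objective progression, so scanning continues under Protocol 5.1.6. A later CR or PR counts for ORR. This route follows from the rules as written.
- *CTCL.* Protocol 13.3.1.4 asks for on-treatment progression to be confirmed 1 to 4 weeks later, because a flare may be temporary. Assessments after a first PD are therefore expected. The SAP does not say how they enter best response, PFS or DOR.
- *Other.* Treatment continued past PD (Protocol 5.2.1 says patients may be withdrawn, not must) or unscheduled scans.

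**3. Effect on DOR.** SAP 4.9.2 gives DOR = (date of first documented progression or death) − (date of first response). If clinical progression comes at time t1 and the first response at t2 > t1, then DOR = t1 − t2 < 0. Off-treatment scans are timed about 12 weeks from the last tumour assessment. For progression dated at end of treatment and a response on the next scan, the value is therefore negative by up to about 12 weeks.

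**4. Size of one reclassified patient.** This is 1/10 = 10 points in a Part 2 cohort of about 10 (Protocol 8.3) and 1/60 = 1.7 points in 60. The SAP's exact 95% interval (Clopper-Pearson) has lower limit Beta(0.025; x, n − x + 1) and upper limit Beta(0.975; x + 1, n − x). The response counts below are illustrations.

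| Responders | ORR | Exact 95% CI |
|---|---|---|
| 3/10 | 30.0% | 6.7 to 65.2 |
| 4/10 | 40.0% | 12.2 to 73.8 |
| 18/60 | 30.0% | 18.8 to 43.2 |
| 21/60 | 35.0% | 23.1 to 48.4 |

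**5. Possible total shift from late responses.** Let f be the share of patients stopping without objective PD and r the chance that such a patient first responds off treatment. The shift in ORR is f × r. The documents give neither value. Assuming f from 10% to 50% and r from 5% to 20%, the shift runs from 0.10 × 0.05 = 0.5 points to 0.50 × 0.20 = 10 points, or 0.3 to 6 patients of 60. With f = 30% and r = 10% it is 3 points (1.8 of 60).

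**The case against.** The strongest reply is that the SAP window is a legitimate choice. Counting responses until new therapy starts is reasonable, and Protocol section 8 leaves technical detail to the SAP. That stands as a defence of the window itself. It does not cover the missing entry in SAP 3.3 or the missing rule for progression. The protocol's DOR, OS and PFS paragraphs each defer censoring detail to the SAP; its ORR paragraph defers nothing.

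Four stronger readings are tempting, and the documents do not support them:
- A reader might infer that a patient with objective PD at week 6 would routinely become a responder on follow-up scans. Scheduled scans stop at objective PD, and the protocol's own cut at discontinuation normally falls at PD as well.
- A reader might infer that the SAP figure can only be equal or higher. Protocol 6.10.1 allows palliative radiation after the first cycle, and SAP 4.7.3 lists radiation among subsequent therapies. If on-study radiation is handled that way, it closes the SAP window early, and a later on-treatment response would count only under the protocol.
- A reader might take ORR as the lead activity measure. It is one of four secondary activity measures, and the primary objectives are safety and dose.
- A reader might infer that the sponsor left out a change it knew about. The SAP was written against Amendment 9, and the amendment number of the supplied protocol is not visible. The omission can be judged only against the supplied text.

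It is also fair to say that a CTCL response after an unconfirmed flare may be intended. If so, the SAP should say so. The different ORR denominators in the two documents are declared in SAP 3.3 and are not part of this point.

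**Conclusion.** The point holds and is minor. Against the supplied protocol, the SAP uses a longer response window and does not list the difference in 3.3. It has no cut at progression, which conflicts with its own PFS and DOR definitions, chiefly for clinical progression followed by scans and for a first unconfirmed PD in CTCL.

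Late off-treatment responses are the main source of any numerical difference; post-progression responses are a narrower one. The SAP ORR will usually be equal or higher. The frequency is not stated and is probably low. The 0.5 to 10 point range rests wholly on assumed values of f and r, and the illustrative intervals in cohorts of 10 overlap almost entirely. The consequence is for the clarity and internal consistency of a descriptive secondary endpoint.

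**What to change.** Use one window in both documents: best response from first dose to the earliest of first documented progression, start of subsequent anticancer therapy or procedure, and data cut-off. Progression should carry the same definition as in PFS and DOR, with explicit statements on whether clinical progression closes the window and whether the first or the confirmed PD counts in CTCL. State whether on-study palliative radiation counts as subsequent therapy for this endpoint. List the change in SAP 3.3.

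Report ORR to treatment discontinuation as a sensitivity row, saying whether the scan at the End of Treatment visit is included.

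The cost is SAP wording, a matching sentence in the protocol at its next amendment, and one extra table row. The downside is that the reported ORR may be slightly lower than under the present SAP rule.
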